#### **Abbreviations**

AAC Area Above the Curve

AE Adverse Event

ALT alanine aminotransferase/serum glutamic pyruvic transaminase (SGPT)

ANCOVA Analysis of Covariance
ANOVA Analysis of Variance

AST aspartate aminotransferase/serum glutamic oxaloacetic transaminase (SGOT)

AUC Area under the concentration – time curve

AUCinf Area under the concentration – time curve from time zero to infinity

Area under the concentration – time curve from time zero to time of last measurable

concentration

BLQ Below the Limit of Quantification

BMI Body Mass Index
BP Blood Pressure
bpm beats per minute

BSI Brief Symptom Inventory

CA Competent authority (also CCMO)

CCMO Central Committee on Research Involving Human Subjects; in Dutch: Centrale

Commissie Mensgebonden Onderzoek

CHDR Centre for Human Drug Research

CI Confidence Interval CK creatine kinase

CL/F Apparent total clearance following extravascular administration

Cmax Maximum concentration
CPM Conditioned Pain Modulation

CV Coefficient of variation

EC Ethics Committee (also Medical Research Ethics Committee (MREC); in Dutch:

Medisch Ethische Toetsing Commissie (METC).

ECG Electrocardiogram

EDTA Ethylene diamine tetra-acetic acid

EEG Electroencephalogram

EMA European Medicines Agency

EU European Union
GCP Good Clinical Practice

ICH International Conference on Harmonization

INR International Normalized Ratio

ISB In Silico Biosciences i.v. Intravenous(ly)

LDH Lactate dehydrogenase

Max Maximum

MED Minimal erythema dose

MedDRA Medical Dictionary for Regulatory Activities

min Minutes
Min Minimum

M3G Morphine-3-Glucuronide M6G Morphine-6-Glucuronide

NONMEM NONlinear Mixed Effects Modelling

SAE Serious Adverse Event
SAP Statistical Analysis Plan
SD Standard Deviation

SEM Standard Error of the Mean

SFMPQ Short Form McGill Pain Questionnaire

SOC System Organ Class

SOP Standard Operating Procedure

SPC Summary of Product Characteristics

SRT Simple Reaction Time
SST Serum Separator Tube

STAI State-Trait Anxiety Inventory

SUSAR Suspected Unexpected Serious Adverse Reaction

pEEG Pharmaco-Electroencephalogram

PDT Pain Detection Threshold
PTT Pain Tolerance Threshold
t½ Terminal Elimination Half-life

 $\begin{array}{ll} t_{\text{lag}} & \text{Absorption lag time} \\ t_{\text{max}} & \text{Time to attain $C_{\text{max}}$} \\ \text{ULN} & \text{Upper Limit of Normal} \\ \text{VAS} & \text{Visual Analog Scale} \\ \end{array}$ 

VVLT Visual Verbal Learning Test
WHO World Health Organization

WMO Medical Research Involving Human Subjects Act; in Dutch: Wet Medisch-

wetenschappelijk Onderzoek met Mensen.

#### 1. Executive Summary

The body of this report consists of a clinical trial protocol for the combination of morphine and nortriptyline in patients with chronic neuropathic pain.

#### 2. Deliverable Report

#### **CLINICAL STUDY PROTOCOL**

A randomized, double-blind, double dummy, placebo-controlled, two-way cross-over study to investigate the analgesic effects and CNS effects of morphine and nortriptyline in patients with chronic neuropathic pains.

#### 2.1 SYNOPSIS

This study is a randomized, double-blind, double-dummy, placebo-controlled, two-way crossover trial designed to evaluate the analgesic efficacy and central nervous system effects of morphine and nortriptyline in patients suffering from chronic neuropathic pain.

#### Rationale

Chronic pain is one of the most prevalent and complex medical conditions in the Western world. In general, around 20% of the population in Europe experiences chronic pain, resulting in a large socioeconomic burden, including the effect on the patient's environment and the health care system. Current pain drug treatment options include opioids, anti-depressants, antiepileptics, benzodiazepines and nonsteroidal anti-inflammatory drugs (NSAIDs).

60% of patients treated for chronic pain responds poorly to the above-mentioned therapies. Prescription of opioids, currently the most effective class of analgesics for moderate to severe chronic pain, has furthermore led to complications related to their adverse effects, including sedation, cognitive side-effects, and drug abuse liability. A solution for this may be by adding a non-opioid analgesic to treatment with an opioid, which may lead to an opioid-sparing effect. For example, therapies with combinations of morphine and anti-epileptics (e.g., pregabalin), selective serotonin and norepinephrine inhibitors (e.g., duloxetine) or anti-depressants (e.g., nortriptyline), may lead to an improved balance of therapeutic benefit and adverse effects, tailored to the needs of individuals and stratified patient groups.

To obtain a better understanding of combination pain therapies a consortium was established through a Horizon 2020 European Union grant: QSPainRelief (H2020-SC1-BHC-2018-2020). The consortium will investigate alternative novel drug combinations with improved analgesic- and reduced adverse effects in the context of a full translational program: from in-silico modelling based on in vitro and in vivo developed results to two healthy volunteer studies and eventually in studies with pain patients. All studies are performed by consortium members (www.qspainrelief.eu).

So far, in silico, in vitro, and preclinical research has been performed by the QSPainRelief consortium to investigate which combination therapy may provide the optimal analgesic-adverse effect profile [Data not yet published]. Data have been gathered in the QSPainRelief model. Initial discussion and results indicate that for this patient with chronic neuropathic pain study morphine (a potent  $\mu$ -opioid receptor) in combination with nortriptyline (a tricyclic antidepressant) may yield improved clinical utility over either drug used as monotherapy.

Nortriptyline is a tricyclic antidepressant (TCA) widely used in the treatment of neuropathic pain conditions, including diabetic neuropathy and postherpetic neuralgia. It exerts its analgesic effects primarily through inhibition of norepinephrine reuptake, with modest serotonergic reuptake inhibition, enhancing descending inhibitory pain pathways in the central nervous system. Nortriptyline also interacts with muscarinic, histaminergic, and  $\alpha$ 1-adrenergic receptors, contributing to both therapeutic and adverse effects. Clinical studies have shown nortriptyline to be effective in improving pain scores in chronic neuropathic pain and it is included in multiple international guidelines as a first-line treatment. Common side effects include dry mouth, dizziness, constipation, and sedation, which may limit dose escalation in some patients.

PainCart® and NeuroCart® are two comprehensive and validated test batteries commonly used in early-phase drug studies to profile pharmacodynamic effects of (novel) drugs. PainCart® consists of an evoked pain test battery that was used previously to amongst others profile morphine, pregabalin and the opioid fentanyl.¹¹ NeuroCart® is a CNS test battery that is used to assess drug-induced changes in CNS functioning. The batteries have previously been used together to evaluate possible synergistic effects of two analgesics, and to determine the CNS and analgesic profile of a novel investigational drug.¹¹¹

The aim of this first human experimental pain study, the QSPainRelief-novel-B-trial, is to investigate the analgesic effects and effects on CNS functioning of morphine and nortriptyline as an analgesic combination in patients with chronic neuropathic pains, compared to each of the two analgesics alone and to placebo.

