#### **Objectives**

The primary objectives are:

[figure not shown]
 To evaluate the analgesic effects of morphine, nortriptyline and the two drugs as combination using PainCart®

The secondary objectives are:

- To evaluate the effects on central nervous system (CNS) functioning of morphine, nortriptyline and the two drugs as combination as measured using NeuroCart®
- To compare the tolerability of morphine alone, nortriptyline alone and the two drugs when given together
- To evaluate the blood pharmacokinetics of morphine, nortriptyline and the two drugs as combination

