#### **Trial Design**

This is a randomized, double-blind, double dummy, placebo-controlled, two-way cross-over study to investigate the pharmacodynamic effects and adverse effects of morphine and nortriptyline in patients with chronic neuropathic pains.

Each study participant will receive the following study treatments:

- Morphine 3 mg IV + 7 mg IV + placebo
- Nortriptyline 75 mg orally + Morphine 3 mg IV + Morphine 7 mg IV

Protocol time Treatments	0h00m	2h00m	5h00m			
1	Placebo	Morphine 3 mg IV	Morphine 7 mg IV			
2	Nortriptyline 75mg	Morphine 3 mg IV	Morphine 7 mg IV			

In total, each subject will be exposed to two treatment options. Each treatment period will consist of one study visit to the clinical research unit. During this visit, arrival to the clinical research unit will be in afternoon of day before dosing (Day-1). In the morning of the next day (Day 1), subjects will receive the study treatment prior which and after which pharmacokinetic (PK) assessments and the pharmacodynamics (PD) will be performed. Subjects will be discharged in the afternoon of Day 2. Each study period will be followed by a wash-out period of at least 7 days and a final follow-up visit 7-14 days after the last dosing day.

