Nortriptyline is a tricyclic antidepressant (TCA) widely used for neuropathic pain conditions such as diabetic neuropathy and postherpetic neuralgia. Its analgesic effects are primarily attributed to potent inhibition of norepinephrine reuptake and moderate inhibition of serotonin reuptake.6a,6b This enhances descending pain inhibitory pathways within the CNS.

Combination analgesic strategies involving opioids and tricyclic antidepressants may offer superior pain relief with a reduced opioid burden. Nortriptyline is a well-established treatment for neuropathic pain and, when used in combination with opioids like morphine, may produce additive or synergistic effects on analgesia.

PainCart® and NeuroCart® are two comprehensive and validated test batteries commonly used in early-phase drug studies to profile pharmacodynamic effects of (novel) drugs. PainCart® consists of an evoked pain test battery that was used previously to amongst others profile morphine, pregabalin and the opioid fentanyl.¹¹ NeuroCart® is a CNS test battery that is used to assess drug-induced changes in CNS functioning. The batteries have previously been used together to evaluate possible synergistic effects of two analgesics, and to determine the CNS and analgesic profile of a novel investigational drug.¹¹

The aim of this experimental pain study is to investigate the analgesic effects and effects on CNS functioning of morphine and nortriptyline as an analgesic combination in patients with chronic neuropathic pains, compared to each of the two analgesics alone and to placebo. This trial aims to characterize these effects in a patient population rather than in healthy volunteers.

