#### **2.4 OBJECTIVES AND ENDPOINTS**

**Table 2.** Objectives and Endpoints

Objectives	Endpoints				
Primary					
To evaluate the analgesic effects of morphine, fluvoxamine and the two	
 
Pressure Pain: Pain Detection Threshold (PDT), Pain Tolerance Threshold (PTT), Area Under the Curve (AUC), post-test Visual Analogue Scale (VAS)
 
				
drugs as combination using PainCart	
 
Heat pain (pre-cold pressor: unexposed/normal and capsaicin-exposed skin) (only for eligible subjects): PDT, and post-test VAS
 
				
	

Cold Pressor: PDT, PTT, Area Above the Curve (AAC), post-test VAS

				
	4. Electrical Stair test: PDT, PTT, AUC, post-test VAS				
	5. Electrical burst test: PDT, PTT, AUC, post-test VAS				
	

Conditioned Pain Modulation (CPM) Response (change from heat pain pre- and post-cold pressor): PDT

				
	
 
Short Form McGill Pain Questionnaire (SFMPQ) for pressure pain, heat pain, cold pressor, electrical stair test and electrical burst test
 
				
Secondary					

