## morphine + nortriptyline versus morphine

All the collected PD endpoint will be analysed with descriptive statistics. However, only PD endpoints collected after start of the first IV bolus injection will be used for the mixed model ANCOVA analysis.

Final analysis of specific PD endpoints (PainCart® and CNS tests) will be performed in sequence to limit the number of tests. Refer to Table 3 and 4 below. Initially, only the parameters listed in the 'first round analysis' column will be analysed following methods described further along this paragraph.

Only in case one or more of the endpoints listed in the 'first round analysis' column reaches statistical significance in any of the contrasts, the endpoints mentioned in the 'second round analysis' will be analysed. Whether to proceed with the 'second round analysis' is evaluated separately for each test.

Due to the large amount endpoints obtained from pEEG, those results will be analysed separately to allow for comprehensive evaluation of all power bands, EEG-derivations taken together.

BSI endpoints will be presented in a frequency table.

**Table 9.** PainCart® endpoints

PainCart® endpoints			
Test	First round analysis	Second round analysis	
Pain pressure	PDT, PTT	AUC, VAS, McGill	
Heat Pain	PDT	VAS, McGill	
Cold pressor	PDT, PTT	AAC, VAS, McGill	
Electrical stair	PDT, PTT	AUC, VAS, McGill	
Electrical Burst	PDT, PTT	AUC, VAS, McGill	
CPM PDT		NA	

**Table 10.** CNS test endpoints

CNS test endpoints			
Test	First round analysis	Second round analysis	
Adaptive tracker	Average performance	NA	
Body sway	Antero-posterior sway	NA	
VAS B&L	Alertness	Mood; calmness	
VAS Bowdle	Feeling High	- Internal perception	
		- External perception	
N-back	- Average reaction time (ms) (two-	- Average reaction time (ms) (zero- and	
	back)	one-back)	
	- Number of correct targets (two-	- Number of correct targets (zero- and	
	back)	one-back)	
	- Number of incorrect targets (two-	- Number of incorrect targets (zero- and	
	back)	one-back)	
	- Number of faulty non-target	- Number of faulty non-target responses	
	responses (two-back)	(zero- and one-back)	
VVLT	- Delayed recall (number correct)	- Immediate recall trial 3 (number	
		correct)	
		- Delayed recognition (number correct)	
		- Delayed recognition (reaction time)	
Eye Movement	- Saccadic peak velocity	NA	
	(degrees/sec)		
	- Saccadic reaction time (sec)		
	- Saccadic Inaccuracy (%)		
	- Smooth pursuit (%)		
Pupillometry	- Pupil/iris ration (left and right)	NA	

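### The aim promises comparison with each drug alone and with placebo, but both listed regimens contain morphine, so only the add-on effect of nortriptyline can be estimated

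*Protocol*

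**What the plan says.** The aim in Protocol 2.1 (Rationale) is to study the two drugs "as an analgesic combination in patients with chronic neuropathic pains, compared to each of the two analgesics alone and to placebo". Section 2.2.1 repeats it: "compared to each of the two analgesics alone and to placebo". The primary objective in the Synopsis is "To evaluate the analgesic effects of morphine, nortriptyline and the two drugs as combination using PainCart". One secondary objective reads "To compare the tolerability of morphine alone, nortriptyline alone and the two drugs when given together".

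The Trial Design part of the Synopsis says "In total, each subject will be exposed to two treatment options". The first of these is "Morphine 3 mg IV + 7 mg IV + placebo"; the second replaces the placebo with oral nortriptyline 75 mg and keeps both morphine doses. Section 2.7.1 lists the same pair and places the boluses at 2 h and 5 h in both.

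Section 2.13.6 plans one contrast, "morphine + nortriptyline versus morphine", and admits to the mixed-model ANCOVA only pharmacodynamic data collected once the first bolus has started. Earlier data are summarised descriptively.

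Three other parts of the protocol bear on the point:

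- The ethics paragraph of the Synopsis poses a narrower question: whether adding nortriptyline improves on morphine alone.
- That paragraph and section 2.3.2 also speak of potentiation. Section 2.7.1 expects synergy or potentiation to be explored in the PK/PD analysis, which section 2.13.6 makes optional.
- Table 1, sections 2.5.2, 2.5.3 and 2.7.1, and Table 3 in 2.10.2 still refer to four periods, occasions or treatments.

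**The concern.** The aim needs four conditions: placebo, nortriptyline, morphine and the combination. The regimen list supplies two. If this stands, three things follow:

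- Any statement about the effect of morphine alone would rest on uncontrolled change from baseline.
- The tolerability comparison would have no nortriptyline-alone experience beyond the first 2 hours.
- A favourable add-on result could be read as potentiation although simple addition would explain it equally well.

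A larger sample cures none of this, because the information is absent rather than imprecise.

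**Working it through.** **Inputs.** The regimens and bolus times come from 2.1 (Trial Design) and 2.7.1. The contrast and the data restriction come from 2.13.6. The assessment times come from Table 1, and the nortriptyline peak time of 2 to 8 h from 2.2.2.

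**The protocol's own figure.** The only power figure is 82.5% in section 2.13.5 (N = 24, CV 30%, 5 s on a mean of 20 s, two-sided 0.05). A normal approximation reproduces that row:

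- SE = 0.30 × √(2/24) = 0.0866
- 0.25 / 0.0866 = 2.887, and 2.887 − 1.960 = 0.927
- power = Φ(0.927) ≈ 0.823

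The same formula does not reproduce the other rows of Table 8, which is a separate matter. The figure belongs to pregabalin minus placebo, and neither of those is a regimen in this trial, so it gives no support to the broader aim.

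**Estimability after the first bolus.** Write the four condition means with parameters (μ, N, M, I), where I is the interaction:

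| Condition | Mean | Observed after 2 h? |
|---|---|---|
| Placebo | μ | no |
| Nortriptyline | μ + N | no |
| Morphine | μ + M | yes |
| Combination | μ + N + M + I | yes |

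The design rows are (1,0,1,0) and (1,1,1,1), of rank 2. A contrast is estimable only if it lies in their row space.

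| Contrast | Estimable? |
|---|---|
| Combination − morphine | yes |
| Combination − nortriptyline | no |
| Combination − placebo | no |
| Morphine − placebo | no |
| Nortriptyline − placebo | no |
| Morphine − nortriptyline | no |
| Interaction I | no |

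One of six pairwise contrasts is available. It equals (0,1,0,1), that is N + I: the plain nortriptyline effect and the interaction enter only as a sum. As an illustration, take the protocol's planning difference of 5 s as the add-on effect. N = 5 with I = 0 (pure addition) and N = 0 with I = 5 (pure potentiation) give identical expected data.

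**The pre-bolus window.** Before 2 h, the second regimen is nortriptyline alone and the first is placebo. Table 1 places one of the six post-dose PainCart rounds there (1 h; the others are at 3, 4, 6, 7.5 and 9 h). NeuroCart falls at 1 h and again at 2 h. The 2 h round coincides with the nominal bolus time, its order relative to the bolus is not clear, and a round takes about 40 minutes. The window closes as the stated peak range opens.

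**If four regimens existed.** With nortriptyline-alone and placebo-only regimens added, the rank becomes 4 and all six contrasts and the interaction are estimable. The interaction's standard error would be √2 times that of a pairwise contrast. For N = 24 and an assumed interaction ratio of 1.25, power would be about 74% if the 30% CV describes a within-subject difference, and about 45% if it is an ordinary within-subject CV.

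**The case against.** The strongest reply is that the inferential plan already fits the regimens. Section 2.13.6 asks one question, the design answers it, and the ethics paragraph of the Synopsis states it. The study is declared exploratory with no formal null hypothesis. This stands to the extent that the fault lies in the aim and objectives, not in the planned contrast. Exploratory status, however, excuses the lack of a formal hypothesis; it does not supply a missing condition.

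A reader might infer that most of the objectives, synergy among them, are unanswerable. The documents do not support that. Synergy is not a listed objective: it appears as background and in the dose justification, and is left to modelling that may or may not be done. Only the tolerability objective names nortriptyline alone. The add-on part of the PainCart, NeuroCart and tolerability objectives can be answered, as can morphine PK with and without nortriptyline.

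A reader might also take the two-regimen design as settled. The four-period and four-treatment wording would fit the broad aim, so the protocol is in conflict with itself about the design. That wording does not rescue the aim, because no nortriptyline-alone or placebo-only regimen is listed anywhere.

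PK/PD modelling could in principle address potentiation, but with these regimens it would have to rely on external monotherapy data or on model assumptions, and the protocol specifies neither for this combination.

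**Conclusion.** The aim in 2.1 and 2.2.1 and the tolerability objective name conditions that neither listed regimen provides during the analysed period. On post-bolus data, one of six pairwise contrasts is estimable and the interaction is not, whatever the sample size. The objectives cannot be answered in full as written; their add-on part can. Potentiation beyond additivity cannot be told apart from simple addition without outside data or assumptions.

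This rests on the two regimens listed in 2.1 and 2.7.1 being the complete set, and on the restriction of the model to post-bolus data. That a positive result would be misreported as synergy is a risk, not something the protocol plans.

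Table 2 names fluvoxamine in its objectives ("To evaluate the analgesic effects of morphine, fluvoxamine and the two" and the CNS, PK and safety rows). That is a separate naming error: it does not bear on estimability and adds no weight here.

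**What to change.** 1. Reconcile the aim, the listed regimens and the number of periods and treatments: 2.1 (Trial Design) and the regimen list in 2.7.1 against Table 1, 2.5.2, 2.5.3, the period wording in 2.7.1, and Table 3. Rewording the aim alone would leave the protocol contradicting itself.
2. If the two listed regimens stand, restate the aim, the objectives and Table 2 as the add-on question. For example: *to estimate the effect of adding nortriptyline to intravenous morphine, compared with intravenous morphine plus placebo, on PainCart endpoints (primary) and on NeuroCart endpoints, tolerability and morphine pharmacokinetics (secondary); nortriptyline pharmacokinetics are described in the presence of morphine.* Remove nortriptyline alone and placebo as comparators.
3. Label the 0 to 2 h data as a descriptive comparison of nortriptyline with placebo, and state whether the 2 h NeuroCart round precedes the bolus.
4. State that the two-regimen comparison does not by itself distinguish potentiation from additivity, and that any PK/PD claim of this kind must name its external data or assumptions.
5. Separately, correct the drug name in Table 2.

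If the two regimens stand, the cost is protocol text and a narrower stated claim. If the broad aim is to be kept, the regimen list is incomplete and wording alone will not repair it.

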#### **Objectives**

The primary objectives are:

[figure not shown]
 To evaluate the analgesic effects of morphine, nortriptyline and the two drugs as combination using PainCart®

The secondary objectives are:

- To evaluate the effects on central nervous system (CNS) functioning of morphine, nortriptyline and the two drugs as combination as measured using NeuroCart®
- To compare the tolerability of morphine alone, nortriptyline alone and the two drugs when given together
- To evaluate the blood pharmacokinetics of morphine, nortriptyline and the two drugs as combination

